#### (4) CFR ( $T_{mn}$ at rest/ $T_{mn}$ at hyperemia)

The indication for PCI will be based on measurement of FFR, the current standard of practice, which will be determined as:

#### (5) FFR ( $P_d/P_a$ at hyperemia)

where  $P_a$  is the aortic pressure measured by the guiding catheter at peak hyperemia. PCI is indicated in stenoses with FFR <0.8.

$T_{mn}$  under basal condition followed sequentially by IMR, FFR and CFR under maximum hyperemia will be measured at 3 separate time points: 1) pre-atherectomy, 2) immediately post atherectomy and 3) at the end of the PCI.

	Screening	Procedure	Post Procedure	Discharge
Consent	X			
Medical History	X			
Randomization	X			
CK/MB			X 	
Troponin I			X 	
Physiological Measurements (FFR)		X 		

X 4-8 hours post procedure; if positive again at 12-18 hours

X Physiological measurements (Total coronary flow, Microvascular resistance, Coronary wedge pressure, Coronary flow reserve and Fractional flow reserve) will be taken before and immediately after atherectomy and at the end of PCI)

**Sample Size:** A clinically important difference would be 20% reduction in IMR in OAS, equating to an IMR difference of 7 (SD=8,  $\alpha$  =0.05 and power=0.80) and requiring a total sample size of 20.

**Projected time for completion:** 1 year. CUMC has a large volume for PCI with ~ 3000 number of PCIs per year including ~250 procedures requiring atherectomy.

**Significance of the results:** If OAS is shown to cause lower disruption and loss of coronary microcirculatory function, the use of this atherectomy device may have significant favorable impact on myocardial recovery and function post PCI as compared to RA, potentially leading to prevention of major adverse cardiovascular events.

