**Inclusion Criteria:**

- 1) Age  $\geq$  18 years
- 2) Patient with an indication for PCI including:
  - i) Angina (stable or unstable),
  - ii) Silent ischemia (a visually estimated target lesion diameter stenosis of  $\geq 70\%$ , a positive non-invasive stress test, or FFR  $\leq 0.80$  must be present),
  - iii) NSTEMI
- 3) Patients will undergo cardiac catheterization and possible or definite PCI with intent to stent using any non-investigational metallic drug-eluting stent (DES)
- 4) Signed written informed consent
- 5) Heavily calcified (severe) lesions necessitating atherectomy.

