### Procedures:

**Physiological indices:** Subjects will be randomized on a 1:1 basis to OAS versus RA. In both groups, we will perform sequential physiological interrogation of the coronary vasculature before and immediately after atherectomy and at the end of PCI, utilizing a direct and robust assessment of microvascular function. This will be achieved by measurement of the mean transit time ( $T_{mn}$ ) of saline using a single pressure-temperature sensor-tipped coronary wire (Certus™ guidewire, St Jude Medical, St Paul, Minnesota). The following parameters will be assessed:

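### Randomization is scheduled before the FFR reading that the protocol says decides the PCI indication, so a randomized patient could yield no post-atherectomy IMR

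*Combined protocol and SAP*

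**What the plan says.** All references are to the combined protocol and SAP.

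- **Treatment rule.** Section (4) CFR says: "The indication for PCI will be based on measurement of FFR, the current standard of practice". Section (5) FFR gives the threshold: "PCI is indicated in stenoses with FFR <0.8".
- **Entry.** Inclusion Criteria item 2 accepts angina and NSTEMI with no FFR condition. For silent ischemia, FFR at or below 0.80 is the last of three alternatives; the other two are a visually estimated stenosis of at least 70% and a positive stress test ("a positive non-invasive stress test, or FFR"). Item 3 leaves treatment open at entry: "Patients will undergo cardiac catheterization and possible or definite PCI with intent to stent". Item 5 requires severe calcification needing atherectomy, which is a separate judgement from FFR.
- **Timing.** The schedule table under section (5) FFR marks Randomization in the Screening column and the row "Physiological Measurements (FFR") in the Procedure column only. The Procedures section plans "sequential physiological interrogation of the coronary vasculature before and immediately after atherectomy and at the end of PCI", and section (5) confirms that the indices "will be measured at 3 separate time points: 1) pre-atherectomy" and at two later points.
- **Sample size.** The Sample Size paragraph is built on IMR (difference 7, SD 8, alpha 0.05, power 0.80), "requiring a total sample size of 20". It makes no allowance for randomized patients without a post-atherectomy IMR.
- **Not stated.** The protocol does not say what happens to a randomized patient whose FFR is 0.8 or higher. It has no instruction to treat anyway, no replacement rule and no analysis population.

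**The concern.** Taken together, these sections let a patient meet every entry criterion, be randomized, and then fail the protocol's own test for PCI. If the test is applied, there is no atherectomy and so no IMR at the second or third time point. If the operator treats anyway, the FFR statement is not followed. The protocol does not choose between these.

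At stake is an avoidable loss of randomized patients from a very small comparison: with 10 per arm, each loss is 10% of an arm. The reading that would prevent it is already planned, but on the schedule it comes after allocation.

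There is also a minor mismatch in the cut-off. The inclusion criteria use 0.80 or below and section (5) uses below 0.8. This matters only for a reading of exactly 0.80, which would satisfy entry but not the treatment rule.

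**Working it through.** **Inputs from the protocol.** IMR difference 7, SD 8, alpha 0.05, power 0.80, total 20, allocation 1:1 (10 per arm), about 250 atherectomy procedures a year at the site.

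**Assumptions.** The protocol names no test, so I use an unpaired two-sided t interval. It gives no FFR distribution, so the share *p* of entrants with FFR of 0.8 or more is varied over 2%, 5%, 10% and 20%, the same in both arms. Severe calcified lesions may put the true share at the low end.

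**1. The plan's own figure.** Per arm, n = 2 × (8/7)² × (1.960 + 0.842)² = 20.5, so 21 per arm or 42 in total. The stated total of 20 is not reproduced. At 10 per arm, two-sided power is about 0.50 by the normal approximation. This is a separate problem and is not argued here. It matters only because it shows there is no slack to absorb losses.

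**2. Cost of each lost patient.** Half-width = t(0.975, n₁+n₂−2) × 8 × √(1/n₁ + 1/n₂).

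| Evaluable | SE | t | Half-width |
|---|---|---|---|
| 10 v 10 | 3.578 | 2.101 (18 df) | 7.52 |
| 10 v 9 | 3.676 | 2.110 (17 df) | 7.76 |
| 9 v 9 | 3.771 | 2.120 (16 df) | 7.99 |

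The target difference is 7, so the half-width exceeds it even with no loss. One loss adds about 0.24.

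**3. Range over the assumed share.** Losses are binomial (10, *p*) in each arm. Expected loss is 20*p*; the chance of at least one is 1 − (1 − *p*)²⁰; patients to consent so that 20 are randomized after the FFR reading is 20/(1 − *p*), rounded up.

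| Assumed *p* | Expected loss of 20 | Chance of at least one | Mean half-width | Consent to randomize 20 |
|---|---|---|---|---|
| 2% | 0.4 | 33% | 7.61 | 21 |
| 5% | 1 | 64% | 7.77 | 22 |
| 10% | 2 | 88% | 8.05 | 23 |
| 20% | 4 | 99% | 8.71 | 25 |

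These rows show what each assumed share would mean. They are not estimates of how often it would happen.

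**4. Bias.** The FFR that would stop treatment is read before either device is used, so the device cannot influence it. Nothing here implies that losses would differ between arms.

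**The case against.** The strongest reply is that no sentence in the protocol withholds PCI at FFR of 0.8 or more. Saying that PCI is indicated below a threshold does not say that other indications lapse above it. Several places suggest that the indication exists at entry: item 2 of the Inclusion Criteria lists angina and NSTEMI as indications in their own right, item 5 requires a lesion needing atherectomy, and the Primary Objectives describe patients in whom PCI and atherectomy are already clinically warranted. The Alternatives section treats FFR as optional outside the trial. On this reading a patient with FFR 0.83 is treated and no IMR is lost.

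The schedule is also coarse. It omits the MRI and the pregnancy test. The lesion criteria require an angiogram, so Screening must include or follow one. Because FFR is one route to entry, some patients may have a reading before allocation.

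Much of this stands. It shows that the text supports two readings and that the rate of loss may be zero. It does not remove the problem. Section (4) says that the indication will rest on FFR, item 3 leaves PCI only possible at entry, and nothing requires an FFR before randomization for angina or NSTEMI entrants. An angiogram is not an FFR.

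A reader might infer that every entrant ought to have FFR at or below 0.80. The documents do not support that as a correction: it would exclude angina and NSTEMI patients whom the protocol chose to admit.

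**Conclusion.** The point holds at low severity. As written, the plan can randomize a patient who, under its own FFR rule, then has no PCI and no post-atherectomy IMR. This depends on the rule governing treatment, which the protocol states in one place and leaves open in others.

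The number affected is unknown and may be none. One loss moves the half-width from 7.5 to 7.8, given SD 8 and an unpaired t interval.

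Two stronger conclusions are tempting and are not supported. One is that substantial loss is to be expected; the percentages above only restate assumed shares. The other is that the comparison would be biased; the deciding measurement precedes the device. What remains is a cheap improvement to the order of steps.

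**What to change.** 1. In the schedule, move Randomization from Screening to the catheterization laboratory, after the pre-atherectomy physiological measurements and after the decision to proceed with atherectomy and PCI.
2. Use one FFR cut-off in the Inclusion Criteria and in section (5) FFR.

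**Cost.** No new measurement is needed. Allocation has to be done in the laboratory. Consented patients who do not proceed become screen failures after exposure to the research wire and adenosine, but they would have had that exposure under the current order too. At assumed shares of 5% to 20%, about 22 to 25 patients would be consented to randomize 20, which is small against about 250 atherectomy procedures a year. If the sponsor intends to treat regardless of FFR, the change does no harm.

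Whether FFR at or below 0.80 should be required of every entrant, or FFR should be only a recorded index, is a clinical choice for the sponsor and is not part of this change.

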Fractional flow reserve (FFR), coronary flow reserve (CFR) and the index of microcirculatory resistance (IMR) will be the primary physiological indices recorded

**Exploratory Objectives:** To compare the incidence of peri-PCI myonecrosis with OAS versus RA, as assessed by measurement of CK-MB and Troponin I and in a subgroup of 20 myocardial edema and late gadolinium enhancement on cardiac MRI..

**Rationale:** Lower incidence of microvascular compromise with OAS may be protective against peri-atherectomy microvascular “plugging” and loss of tissue perfusion, and thereby may result in a reduction in peri-PCI myocardial necrosis, potentially protecting left ventricular function. In patients undergoing elective PCI, IMR has been shown to

independently predict PCI-related microvascular damage and peri-procedural myonecrosis.

**Trial Design:** Randomized, prospective, single-center, investigator initiated, study at Columbia University Medical Center (CUMC).

**Sample Size:** 20

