**General Exclusion Criteria:**

- 1) Estimated creatinine clearance  $<30$  ml/min using Cockcroft-Gault equation, unless the patient is on dialysis;
- 2) STEMI within 24 hours of initial time of presentation to the first treating hospital, whether at a transfer facility or the study hospital.
- 3) PCI within 24 hours preceding the study procedure.
- 4) Cardiogenic shock (defined as persistent hypotension (systolic blood pressure  $<90$  mm/Hg for more than 30 minutes) or requiring pressors or hemodynamic support, including IABP, at time of procedure.
- 5) Mobitz II second degree or complete heart block
- 6) Malignant ventricular arrhythmias requiring treatment
- 7) Pulmonary edema defined as patient with shortness of breath, evidence of volume overload on physical exam, and crepitations on physical exam ( $>1/3$  of lungs) or radiographic interstitial or alveolar pulmonary edema
- 8) Subject is intubated.
- 9) Known LVEF  $<35\%$ .
- 10) Severe valvular disease (e.g. severe mitral regurgitation or severe aortic stenosis)
- 11) Patient is participating in any other investigational drug or device clinical trial that has not reached its primary endpoint.
- 12) Women who are pregnant or breastfeeding (women of child-bearing potential must have a negative pregnancy test within one week before treatment).

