#### **Alternatives**

Patients who do not consent to participate in the research will be treated with whichever device the operator prefers (OAS versus RA) with or without FFR and will not undergo FFR. All other procedures are standard of care.

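### CK-MB and Troponin I are scheduled only after the procedure although NSTEMI patients are eligible, so elevation already present can be counted as peri-PCI myonecrosis in the exploratory comparison

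*Combined protocol and SAP*

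**What the plan says.** The Exploratory Objectives include this aim: "To compare the incidence of peri-PCI myonecrosis with OAS versus RA, as assessed by measurement of CK-MB and Troponin I". They add MRI "in a subgroup of 20 myocardial edema and late gadolinium enhancement on cardiac MRI", without saying when the scan is done.

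The schedule table (end of the section on FFR) marks CK/MB and Troponin I under Post Procedure only; the Screening and Procedure cells are empty. Footnote 1 gives the timing: "4-8 hours post procedure; if positive again at 12-18 hours".

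Inclusion Criteria item 2(iii) admits NSTEMI with no time window and no condition on marker levels. The nearest items in the General Exclusion Criteria are "STEMI within 24 hours of initial time of presentation to the first treating hospital" and "PCI within 24 hours preceding the study procedure". Neither concerns raised CK-MB or troponin.

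For the physiological indices the plan does state a baseline. Under Procedures they are taken "before and immediately after atherectomy and at the end of PCI".

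**The concern.** Incidence of peri-PCI myonecrosis is a statement about injury caused by the procedure. To attribute a raised marker to the procedure, one must know the level beforehand. An NSTEMI patient may arrive with markers already raised and still be above the limit 4 to 8 hours after PCI. With no pre-procedure value and no definition of a positive result, that patient can be counted as an event whatever the device did.

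At stake is the plan's biomarker evidence for the link, drawn in the rationale below the Exploratory Objectives, between less microvascular compromise and less myocardial necrosis. A sample that was not drawn before the procedure cannot be recovered later.

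**Working it through.** **Step 1: does any other text supply the baseline?** The plan states no CK-MB or troponin figure to reproduce, so the first check is a reading.

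- *Schedule table.* It is abbreviated. General Exclusion Criteria item 12 requires that "women of child-bearing potential must have a negative pregnancy test within one week before treatment", and the table has no row for that test. An empty cell is therefore weak evidence by itself. But the pregnancy test is stated elsewhere in the text; a pre-procedure marker is stated nowhere.
- *Alternatives.* "All other procedures are standard of care" does not say that routine marker values will be abstracted or used.
- *Footnote 1.* Both draws follow the procedure, and the second depends on the first being positive. No rule says how the two values separate old from new injury.
- *MRI.* There is no stated timing and no schedule row, so no pre-procedure scan is stated.
- *Definitions.* No threshold, no change-from-baseline rule, and no handling of patients raised at entry.

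**Step 2: average effect.** Let q be the share of patients already positive and p the true procedural incidence, with q equal in both arms in expectation.

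Observed incidence = q + (1-q)p, so observed difference = (1-q) × true difference.

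The documents give neither q nor p. Assume a true incidence of 20% (OAS) and 40% (RA):

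| q | OAS | RA | Difference |
|---|---|---|---|
| 0% | 20% | 40% | 20 points |
| 10% | 28% | 46% | 18 points |
| 20% | 36% | 52% | 16 points |
| 30% | 44% | 58% | 14 points |

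If NSTEMI patients are the only source, q is the NSTEMI share times the fraction still positive. With half still positive, NSTEMI shares of 10%, 20% and 30% give q = 5%, 10% and 15%, and differences of 19, 18 and 17 points.

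**Step 3: chance imbalance.** Inputs: 20 patients (Sample Size) and 1:1 randomization (Procedures), taken as 10 per arm. If K of the 20 have NSTEMI, the number in one arm is hypergeometric. Probability that the arms differ by at least 2 such patients:

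- K=2: 1 - 100/190 = 47%
- K=3: 2 × 120/1140 = 21%
- K=4: 1 - 2025/4845 = 58%
- K=5: 1 - 10800/15504 = 30%
- K=6: 1 - 14400/38760 = 63%

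The values alternate because with even K every unequal split is a difference of at least 2, while with odd K the most even split differs by 1. A difference of 4 or more has probability 0%, 9% (420/4845) and 14% (5460/38760) for K = 2, 4 and 6.

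**Step 4: what an imbalance can do.** Take K=4 split 3 v 1, which has probability 2 × 120 × 10/4845 = 50% over both directions. Expected incidence in an arm with k NSTEMI patients, a fraction f of them still positive, is kf/10 + (1 - kf/10)p.

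| True incidence (OAS v RA) | NSTEMI (OAS v RA) | f = 1 | f = 0.5 |
|---|---|---|---|
| 20% v 40% | 3 v 1 | 44% v 46%: 2 points | 32% v 43%: 11 points |
| 20% v 40% | 1 v 3 | 28% v 58%: 30 points | 24% v 49%: 25 points |
| 20% v 20% | 3 v 1 | 44% v 28%: 16 points | 32% v 24%: 8 points |

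For scale, with 20% in both arms and no contamination, the standard error of the difference is √(2 × 0.2 × 0.8/10) = 0.179, about 18 points.

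**Step 5: power.** The plan names no test. Full enumeration of two binomials, 10 per arm, two-sided 0.05, true 20% v 40%, at q = 0, 10%, 20% and 30%: uncorrected chi-square 13.1%, 11.0%, 9.6% and 8.3%; Fisher's exact test 5.8%, 4.6%, 3.8% and 3.1%.

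**The case against.** **NSTEMI status is known.** It is an enrolment indication, and Medical History is recorded at Screening. A reader might infer that carried-over elevation could never be told apart from a device effect. The documents do not support that: an imbalance in NSTEMI patients would be visible, and a table by indication would be possible. What remains is that no such analysis is planned and that raised baselines from other causes would be missed.

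**Routine care may supply a value.** For NSTEMI patients it may well. The plan does not say that it is collected, at what time, or how it is used, and the missing definition would remain in any case.

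**Randomization balances the problem.** It does in expectation, so a reader who infers a systematic bias toward one device goes too far. Balance in expectation does not remove the inflated incidence or the diluted difference, and with 10 per arm the realized split may be uneven.

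**The harm is small next to ordinary noise, and every size is assumed.** This stands. The 16-point null shift needs 4 NSTEMI patients, a 3 v 1 split and all four still positive, and it is still below one standard error. The calculations also apply one persistence fraction to CK-MB and troponin alike, for which the documents give no basis. The comparison could not support a firm device conclusion with or without a baseline. Low power does not make the incidences interpretable, though, and they will be read descriptively.

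**Conclusion.** The concern holds as a minor point and a cheap improvement. The textual gap is clear: post-procedure markers only, NSTEMI eligible, raised markers not excluded, and no definition of a positive result or of myonecrosis. The size of the harm is not known, because the documents give no NSTEMI share, persistence fraction or myonecrosis rate. Steps 2, 4 and 5 are illustrations under stated assumptions. Step 3 rests only on 10 patients per arm and an assumed NSTEMI count.

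A reader might also infer that the main result is compromised. It is not: the IMR comparison does not use these markers and has its own pre-atherectomy measurement.

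**What to change.** - **Schedule.** Add one pre-procedure CK-MB and Troponin I sample for every patient, at the same point for all (for example at vascular access, before atherectomy). An earlier clinical value of unstated timing is not an adequate substitute, since it need not reflect the level when the procedure starts.
- **Definition.** Define peri-PCI myonecrosis as a rise relative to that sample, with the threshold fixed before enrolment and a stated rule for patients already raised at entry. State what counts as positive for the repeat draw.
- **Analysis.** Keep incidence as the stated exploratory endpoint. As supportive analyses, report incidence in patients with a normal baseline and compare post-procedure marker levels adjusted for baseline.

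Cost: one extra tube per patient, one more entry in the schedule for each marker, and a short definition. The normal-baseline analysis will use fewer than 20 patients if any are raised at entry; how many are lost cannot be told from the documents. The baseline-adjusted comparison can keep every patient who has both values. The fix makes the incidences interpretable but does not cure the low power.

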#### Preliminary results:

Table 1. Physiological findings\*

	OAS (n=6)	RA (n=4)	P
Post-atherectomy			
Coronary Flow (1/s)	1.78±.21	1.41±.62	0.25
Index of microcirculatory resistance (a.u)	21±6	31±7	0.04
Coronary wedge pressure (mmHg)	21±6	27±6	0.15

± standard deviation; \*preliminary nonrandomized data.

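### The sample-size inputs (IMR difference 7, SD 8, total 20) give about 46% power, not the stated 80%, and the mean linking 20% to 7 units is not given

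*Combined protocol and SAP*

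**What the plan says.** The Sample Size paragraph, printed after the schedule of assessments in the Combined protocol and SAP, sets the target effect: "A clinically important difference would be 20% reduction in IMR in OAS, equating to an IMR difference of 7". It gives SD 8, alpha "0.05 and power=0.80", and concludes "requiring a total sample size of 20". The overview near the start of the document also gives 20. Allocation is equal: "Subjects will be randomized on a 1:1 basis to OAS versus RA". That makes 10 patients per arm.

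The paragraph does not state the reference mean for the 20%, the source of the SD, whether alpha is one- or two-sided, or which of the three IMR measurements (before atherectomy, just after it, end of PCI) the 7 units refer to.

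The only IMR means in the document are in Table 1 under Preliminary results, after atherectomy: 21±6 for orbital atherectomy (OAS, n=6) and 31±7 for RA (n=4). The footnote calls them "preliminary nonrandomized data". The Sample Size paragraph does not refer to that table.

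**The concern.** The sentence does two things that a reader cannot reproduce. It derives a total of 20 from a difference of 7 and an SD of 8, although a standardised difference of 7/8 = 0.875 at 80% power needs roughly twice that number. It also converts a percentage into units without giving the mean that the conversion needs.

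The first is the one with consequences. If the power is under one half, a true effect of the size called clinically important would be missed more often than found. A reader who trusts the 80% figure would then take a non-significant result as evidence against that effect, when the trial could not reliably show it. The second leaves the yardstick unclear: 20% and 7 units are the same target only at one particular RA mean, and the plan does not give it.

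**Working it through.** **Inputs.** From the Sample Size paragraph: difference 7, SD 8, alpha 0.05, power 0.80, total 20. From Procedures: 1:1 allocation, so n = 10 per arm. Sidedness is not stated, so both are shown. No dropout allowance is stated, so none is used.

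**1. Reproducing the stated total of 20.** The normal approximation for two independent means is n per arm = 2(z_alpha + z_power)² × SD² / difference².

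- Two-sided: 2 × (1.960 + 0.842)² × 64/49 = 20.5, so 21 per arm, total 42. The t-test needs 21.5, so 22 per arm, total 44.
- One-sided: 2 × (1.645 + 0.842)² × 64/49 = 16.2, so 17 per arm, total 34. The t-test also gives 34.

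Neither gives 20.

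**2. Power with 10 per arm for 7 units.** The noncentrality is 7 / (8 × √(2/10)) = 7/3.578 = 1.957, on 18 degrees of freedom.

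| Test | Normal approximation | t-test |
|---|---|---|
| Two-sided 0.05 | 50% | 46% |
| One-sided 0.05 | 62% | 59% |

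**3. Detectable difference with 10 per arm.** For 80% power, two-sided, the t-test needs a standardised difference of 1.325. Times SD 8 this is 10.6 units, which is 10.6/35 = 30% of 35 or 10.6/31 = 34% of 31. The normal approximation gives 10.0 units.

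**4. Could another reading give 20?**

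- *20 per arm.* Power for 7 units would be 77% by t-test and 79% by normal approximation. This is close to 80%, but the text says 20 in total.
- *A difference of 10*, as observed in Table 1 (31 − 21), with SD 8. The normal approximation gives 11 per arm, total 22, and 79.8% power at a total of 20 (75% by t-test). This is also close, but the text says 7.
- *A one-sample or paired formula with SD 8.* This gives 11 (13 by t-test) and does not fit two randomized arms.
- *A smaller SD.* For a total of 20 with a difference of 7, the SD would have to be about 5.6 (normal approximation) or 7/1.325 = 5.3 (t-test). The text says 8.

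**5. The percentage and the units.**

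- Implied RA mean: 7/0.20 = 35.
- On the Table 1 RA mean: 0.20 × 31 = 6.2 units, and 7/31 = 22.6%.
- For 6.2 units with SD 8, two-sided t-test: power 37% with 10 per arm; 80% needs 28 per arm, total 56.
- Precision of the 31: the 95% interval is 31 ± 3.18 × 7/√4 = 31 ± 11.1, about 20 to 42. It includes 35.

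**The case against.** A reader might infer more from the second part: that the plan declares a 20% effect but sizes the trial on a larger one, because 7 units is 22.6% of the protocol's own RA mean. The documents do not support that. The Sample Size paragraph does not cite Table 1, and its other inputs do not match the table either: SD 8 against 6 and 7, and a difference of 7 against an observed 10. Within the sentence, 20% and 7 units agree if the mean is 35. The value 31 comes from four nonrandomized patients at one of three time points, and its interval covers 35. So 35 is undocumented, not contradicted, and a clinically important difference need not be tied to a pilot mean. This objection stands in full. The 37% is therefore a what-if figure.

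Against the power finding, the best case is that the sponsor intended a one-sided test or an analysis more efficient than a plain t-test. A one-sided test reaches only 59%. Adjustment for pre-atherectomy IMR could help, since IMR is also measured then. As a rough guide, cutting the SD from 8 to 5.3 needs 8 × √(1 − r²) = 5.3, a correlation r of about 0.75 between the two measurements. The documents describe no such adjustment and give no correlation.

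It is also tempting to infer how the 20 arose, either as a per-arm number reported as a total or from the observed difference of 10. Both come close numerically, but nothing in the text says which, if either, happened.

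**Conclusion.** The 80% power claim is wrong on the plan's own inputs. For an IMR difference of 7 with SD 8 and 10 per arm, power is about 46% (two-sided t-test) or 59% (one-sided), and 80% would need a total of about 44 or 34. This assumes a comparison of two independent means, no dropout and no covariate adjustment; dropout would lower the power further. The conclusion does not depend on sidedness or on the choice between t-test and normal approximation.

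The missing reference mean is a lesser gap in reporting. The sentence implies an RA mean of 35 without stating or sourcing it. Supplying 35 would not repair the power claim, because the shortfall is already present at 7 units. If the true RA mean were near 31, a 20% reduction would be 6.2 units and power about 37%.

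**What to change.** Rewrite the sample-size sentence so that it:

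- replaces the 80% claim with the power that 20 patients give for 7 units (about 46% two-sided with SD 8), or with the difference detectable at 80% power (about 10.6 units two-sided, which is 30% of 35 or 34% of 31);
- states the assumed RA mean, its source and the IMR time point, so that the percentage and the units agree;
- states whether alpha is one- or two-sided, and confirms that 20 is the total and not the number per arm.

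If the sponsor relies on a baseline-adjusted analysis, it should name the analysis and the assumed correlation, and base the power on them.

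The cost is one sentence and a less favourable stated power. No more patients are needed if the 80% target for 7 units is dropped. Keeping that target would mean about 44 in total two-sided, or 34 one-sided.

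### The stated inputs (IMR difference 7, SD 8, alpha 0.05, power 0.80) require 44 patients two-sided or 34 one-sided, not 20; with 20 patients power is 46% or 59%.

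*Combined protocol and SAP*

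**What the plan says.** The calculation is in the Sample Size paragraph near the end of the section headed (5) FFR. It sets the target effect: "A clinically important difference would be 20% reduction in IMR in OAS, equating to an IMR difference of 7". It then gives the SD as 8 and closes with "0.05 and power=0.80) and requiring a total sample size of 20". The same total appears in the trial synopsis, after Trial Design: "Sample Size: 20".

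The design is two parallel arms. Under Procedures: "Subjects will be randomized on a 1:1 basis to OAS versus RA". A total of 20 therefore means 10 per arm.

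IMR is recorded three times. With the other indices it "will be measured at 3 separate time points: 1) pre-atherectomy, 2) immediately post atherectomy and 3) at the end of the PCI". The plan does not say which time point the calculation refers to. It also names no test, sidedness, baseline adjustment, correlation or dropout allowance.

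The Exploratory Objectives separately plan CK-MB and troponin and, "in a subgroup of 20 myocardial edema and late gadolinium enhancement on cardiac MRI".

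**The concern.** The paragraph supplies both its inputs and its answer, so it can be checked without any outside source. The standardized difference is 7/8 = 0.875. That is large, but 10 per arm is too few to detect it with 80% power.

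IMR is one of the primary indices and the only one used to size the trial. If the true difference is the one the protocol itself calls clinically important, a two-sided test on 20 patients would miss it more often than not. Readers told that power was 80% could take a non-significant result as evidence that the devices have similar microvascular effects, which the data could not support.

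**Working it through.** **Inputs.** From the Sample Size paragraph: difference 7, SD 8, alpha 0.05, power 0.80, total 20. From Procedures: 1:1 allocation, so n = 10 per arm. Sidedness is not stated, so both versions are run. The SD is taken as the between-patient SD of whatever IMR quantity is compared; if 8 is the SD of a change from baseline, the arithmetic is the same.

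**Step 1. Attempt to reproduce 20.** Normal approximation, per arm:

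n = 2 × (z_alpha + z_power)² × (SD/difference)²

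- Two-sided: 2 × (1.960 + 0.842)² × (8/7)² = 20.5, so 21 per arm, 42 in total.
- One-sided: 2 × (1.645 + 0.842)² × (8/7)² = 16.2, so 17 per arm, 34 in total.

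Neither gives a total of 20. The two-sided per-arm figure of 20.5 is close to it.

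**Step 2. Exact two-sample t-test (noncentral t), standardized difference 0.875.**

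| Per arm | Total | Power, two-sided | Power, one-sided |
|---|---|---|---|
| 10 | 20 | 45.7% | 59.4% |
| 16 | 32 | 66.8% | 78.0% |
| 17 | 34 | 69.6% | 80.3% |
| 20 | 40 | 76.9% | 85.8% |
| 21 | 42 | 79.0% | 87.3% |
| 22 | 44 | 80.9% | 88.7% |

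The required total is 44 two-sided or 34 one-sided. A simulation of 400,000 trials at 10 per arm gave 45.6% and 59.3%. The normal approximation puts two-sided power at 10 per arm at 49.9%, still far from 80%.

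**Step 3. What 10 per arm can detect with 80% power.** The standardized difference must be 1.325 (two-sided) or 1.156 (one-sided).

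- Difference at SD 8: 1.325 × 8 = 10.6, or 1.156 × 8 = 9.25 (9.3 rounded).
- SD at a difference of 7: 7/1.325 = 5.28, or 7/1.156 = 6.05.

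**Step 4. Precision.** The 95% CI half-width is t(0.975, df) × SD × √(2/n).

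- 10 per arm: 2.101 × 8 × √(2/10) = 7.5. Centred on 7, the interval runs from about -0.5 to 14.5.
- 22 per arm: 4.9.

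**Step 5. Other routes to 20.**

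- *Paired or one-sample test:* needs about 13 (two-sided) or 10 (one-sided) patients, and does not fit parallel arms.
- *Adjustment for pre-atherectomy IMR, one post-treatment value:* the residual SD is 8 × √(1 − r²) with 17 degrees of freedom. Reaching 80% with 10 per arm needs r of about 0.75 (two-sided) or 0.66 (one-sided). The plan states neither the adjustment nor a correlation.
- *Per-arm figure written as a total:* 20 per arm is 40 in total, with 76.9% power two-sided or 85.8% one-sided.

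**The case against.** The strongest defence is the pilot in Table 1 of Preliminary results. Post-atherectomy IMR was 21±6 with OAS (n=6) and 31±7 with RA (n=4), a difference of 10 with pooled SD √((5×36 + 3×49)/8) = 6.4. For that effect, 10 per arm gives about 91% power two-sided, or about 75% with SD 8. So 20 patients is not shown to be inadequate for an effect as large as the investigators had observed, and that part stands. But the pilot is small and nonrandomized, and its difference is not the one the protocol powers for. Combining the pilot SD of 6.4 with the stated difference of 7 gives about 64% power two-sided, or 76% one-sided.

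A second defence is that the correlations in Step 5 assume a single post-treatment value, while two are planned. Suppose all three IMR values are equally correlated with SD 8, the difference is 7 at both later points, and their mean is adjusted for baseline. The correlation needed two-sided then falls to about 0.61. One-sided, any non-negative correlation suffices: the variance factor (1 + r)/2 − r² peaks at 0.5625, where power is 80.5%. This is correct as arithmetic, but the plan states no such analysis, so it does not explain the published calculation.

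Third, if 20 was meant per arm and the test is one-sided, 40 patients would exceed 80% power. That also stands, but the text says total, the synopsis repeats 20 as the trial size, and no one-sided test is declared.

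Finally, this is a small single-center physiological study, and nothing in the documents obliges it to be larger. That bears on the remedy, not on the error.

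**Conclusion.** The concern holds. On the plan's own inputs the required total is 44 (two-sided t-test) or 34 (one-sided), against 20 stated. Power at 20 is 46% or 59%, against 80% stated. The gap is too large to come from rounding or choice of formula, and no two-arm calculation using only the stated inputs gives 20.

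This rests on an unadjusted comparison of one IMR quantity between two equal arms, SD 8 in each, and no dropout; any dropout allowance would raise the requirement. A per-arm number reported as a total is the most plausible origin, since the normal approximation gives 20.5 per arm, but that is an inference.

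The wording of the MRI subgroup, which equals the whole trial, is a separate and minor inconsistency. It does not affect the power calculation.

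**What to change.** Replace the Sample Size paragraph with one that matches the design. Suggested text:

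> With 20 patients (10 per arm), SD 8 and two-sided alpha 0.05, power is 46% for an IMR difference of 7 and 80% for a difference of 10.6. The comparison is an unadjusted two-sample t-test of IMR at [named time point]. The result will be reported with its 95% confidence interval (expected half-width about 7.5), and a non-significant result will not be read as no difference.

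The variations depend on what was intended:

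- If the test is one-sided, say so and give 59% and 9.3.
- If a smaller SD or a baseline-adjusted analysis was the basis for 20, state the analysis with the SD or correlation used and its source.
- If 20 was meant per arm, write a total of 40 with 77% power two-sided (86% one-sided) and correct the synopsis.

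Separately, state whether MRI is planned for all patients or for a specified smaller number.

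The restatement costs only wording and a less favourable stated power. Moving to 40 doubles enrolment. Keeping 80% power on the stated inputs needs 44 − 20 = 24 more patients two-sided, or 34 − 20 = 14 more one-sided.
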